## 12.2.2 Secondary efficacy analysis

Response will be assessed using the Uniform response criteria set forth by the International myeloma working group (IMWG) (See Appendix II). Frequencies and percentages will be used to summarize for all response categories. The response in this trial is defined as complete remission (CR), stringent complete remission (SRC), very good partial remission (VGPR) and partial remission (PR). The response rate for patients treated with single agent lenalidomide, lenalidomide and prednisone and lenalidomide and low dose dexamethasone will be calculated as the percentage of responders, and the 95% confidence interval will be calculated using the exact binominal method. Logistic regression will be used to investigate relationships of the response rates with baseline and other relevant covariates, if appropriate.

Overall survival (OS) is defined as the time from study entry to death of any cause. The OS curves will be estimated by the Kaplan-Meier method. Median and its 95% confidence intervals will be estimated. The effect of baseline and other relevant covariates will be investigated with Cox regression models, when appropriate. Confidence intervals for the survival probabilities at different points will be constructed as needed. The PFS curve for the patients treated with single agent lenalidomide will also Version. 6 date 4/15/2016

## 12.2.3 Safety analysis

The following safety analyses will be performed using data from all subjects who receive any study drug. Adverse events will be classified using the MedDRA classification system. The severity of the toxicities will be graded according to the NCI CTCAE v 4.0 whenever possible.

In the by-subject analysis, a subject having the same event more than once will be counted only once. Adverse events (AE) will be summarized by worst NCI CTCAE grade. The patient incidence of AEs will be summarized by system organ class, preferred term, severity and relationship to study drug. Adverse events leading to death or to discontinuation from treatment, events classified as NCI CTCAE v 4.0 grade 3 or higher, study-drug-related events, and serious adverse events will be listed separately. Laboratory data will be graded according to NCI CTCAE v 4.0 severity grade. Cross tabulations will be provided to summarize frequencies of abnormalities. The physical examine results (such as blood pressure, pulse, temperature) at each visit will be summarized using descriptive statistics.

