## **Secondary:**

 To evaluate the efficacy of single agent lenalidomide in patients with standard risk multiple myeloma Page 5 of 86 Confidential

2. To evaluate the safety and efficacy of the combination of lenalidomide and prednisone in non responders to single agent lenalidomide

3. To evaluate markers of lenalidomide induced tumor immunity in patients treated with single agent lenalidomide

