#### STUDY DESIGN:

This is a multi-center, single-arm, phase 2, open-label study of lenalidomide [Revlimid® (R)] based therapy in older adults with standard risk multiple myeloma. After enrollment patients will receive single agent lenalidomide. Responders (minimal response or better) after 2 cycles will continue present therapy until disease progression or intolerable toxicity. Patients with stable disease after 2 cycles will receive prednisone (100 mg orally on days 1 to 5 of each cycles) in addition to lenalidomide. Patients with evidence of disease progression after 2 cycles of single agent lenalidomide will receive low dose dexamethasone (40 mg weekly) in addition to lenalidomide. Patients not receiving low dose dexamethasone and with disease progression at any time during the study will be eligible to receive low dose dexamethasone in combination with lenalidomide. Patients on lenalidomide and low dose dexamethasone who experience disease progression at any time during the study will be taken off study and treated with alternative therapies..

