## **Secondary:**

1- The response rate of older adults with mildly symptomatic multiple myeloma to single agent lenalidomide, lenalidomide prednisone and lenalidomide low dose dexamethasone in patients with suboptimal responses to lenalidomide monotherapy

- 2- The toxicity profile of these lenalidomide based combinations
- 3- The progression free survival of patients treated with single agent lenalidomide
- 4- The 1 year overall survival (OS) of older adults with mildly symptomatic multiple myeloma treated on this response adapted approach

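### Section 12.2.3 plans adverse event summaries only for all treated subjects pooled, with no split by regimen at onset, although secondary objective 2 and secondary endpoint 2 need one

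*Combined protocol and SAP*

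**What the plan says.** The safety questions are partly about regimens. In the synopsis, secondary objective 2 is "To evaluate the safety and efficacy of the combination of lenalidomide and prednisone in non responders to single agent lenalidomide". Secondary endpoint 2, in the synopsis and again in Section 5, is "The toxicity profile of these lenalidomide based combinations".

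The safety analysis in Section 12.2.3 is not about regimens:

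- Population: "The following safety analyses will be performed using data from all subjects who receive any study drug".
- Counting, in the by-subject analysis: "a subject having the same event more than once will be counted only once".
- Grade: "Adverse events (AE) will be summarized by worst NCI CTCAE grade".
- Table dimensions: "The patient incidence of AEs will be summarized by system organ class, preferred term, severity and relationship to study drug".

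It also lists separately the events that are fatal, lead to discontinuation, are grade 3 or higher, are drug-related or are serious. None of these listings is defined by regimen.

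Patients change regimen during the study. All start on lenalidomide alone, and stable disease after 2 cycles leads to added prednisone. In addition, "Patients not receiving low dose dexamethasone and with disease progression at any time during the study will be eligible to receive low dose dexamethasone" (synopsis, Study Design). One patient can therefore contribute time to two or three regimens.

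**The concern.** An objective and an endpoint ask what happens to patients while they take a combination. The planned tables answer a different question: what happens to patients at any point under the strategy. Two things follow from the pooled count.

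- An event that first occurs on lenalidomide alone and recurs at the same or a lower grade after a steroid is added contributes nothing further.
- An event that occurs only on a combination is divided by all treated patients, most or many of whom may never have received that combination.

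If the plan is followed as written, the report will have no incidence figure for lenalidomide-prednisone, although its safety is a named objective, and none for lenalidomide-dexamethasone. Section 6.2 presents prednisone as the better tolerated steroid, so readers will look for these figures.

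**Working it through.** **Is the split supplied anywhere else?**

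| Section | What it gives | By regimen? |
|---|---|---|
| 12 (opening) | Number and percentage of patients on each of the three regimens | Yes, but patients only |
| 12.2.2 | "The response rate for patients treated with single agent lenalidomide, lenalidomide and prednisone and lenalidomide and low dose dexamethasone will be calculated" | Yes |
| 12.2.5 | Antibody titers by treatment and time point | Yes |
| 12.2.3 | Adverse events | No |
| 12.2.4 | Adverse event proportions, Moffitt versus South Korea | No, by site group |

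Relationship to study drug does not fill the gap. Section 9.7 asks for a single relationship to study drug on each report, not one per agent. Section 12.2.3 reads as complete, so the omission does not look like lost text.

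**The plan's own figures.** The plan states no figure for regimen-level safety. Its one precision figure is in Section 12.1: 73.4-92.9% for 85% of 60. The exact binomial 95% interval for 51/60 is 73.4% to 92.9%, which agrees. The intervals below use the same method.

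**Dilution of a combination-only event.** Let f be the fraction of treated patients who receive a combination and p the incidence among them. If the event occurs nowhere else, the pooled table shows f × p. The documents do not give f, so I assume 20% to 50%.

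- f = 0.20 (12 of 60): pooled incidence is 0.20p, one-fifth of the true rate. With p = 20%, it reads 4%.
- f = 0.50 (30 of 60): pooled incidence is 0.50p, one-half. With p = 20%, it reads 10%.

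The ratio depends only on f, so it is the same for Moffitt's 30 patients alone.

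**Mixing within a patient.** Assume 5% incidence on lenalidomide alone and, independently, 20% after moving to a steroid regimen. The once-per-subject pooled incidence is 0.05(1 − f) + f[1 − (0.95 × 0.80)] = 0.05(1 − f) + 0.24f.

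- f = 0.20: 0.040 + 0.048 = 8.8%.
- f = 0.50: 0.025 + 0.120 = 14.5%.

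The table shows neither the 5% nor the 20%, and its value moves with f.

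**Precision of a by-regimen table.** With no events in n patients, the exact two-sided 95% upper limit is 1 − 0.025^(1/n). The chance of seeing at least one case of a 10% toxicity is 1 − 0.9^n.

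| Patients on the regimen | Upper limit with 0 events | Chance of at least one case at 10% |
|---|---|---|
| 6 (20% of 30) | 45.9% | 47% |
| 15 (50% of 30) | 21.8% | 79% |
| 12 (20% of 60) | 26.5% | 72% |
| 30 (50% of 60) | 11.6% | 96% |

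**The case against.** **Once-per-subject counting is standard.** This stands. The rule is not the fault and could equally be applied within regimen. Section 12.2.3 does not say that the count runs over the whole study; that is inferred from a pooled population with no period or regimen named.

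**Steroid toxicity is not wholly hidden.** A reader might infer that the plan conceals it. The documents do not support that. An event that worsens after a steroid is added is counted at its worse grade, and severe, serious and drug-related events are listed separately. Section 9.7 requires administration dates on adverse event reports, so the limit lies in the planned tables and not in the data. Listings still give no incidence by regimen.

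**Only one combination is in an objective.** A reader might take dexamethasone toxicity to be a stated objective too. Objective 2 names only lenalidomide-prednisone; the dexamethasone combination enters through endpoint 2.

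**The pooled table suits the rationale.** A reader might infer that pooling undermines the argument in Section 6.2 for less toxicity from less steroid. That argument is about the whole strategy against lenalidomide with low-dose dexamethasone, and whole-strategy incidence is the relevant quantity. The pooled table should therefore keep its standing.

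**The size is uncertain.** It is tempting to take regimen numbers from the single-agent study in Section 4.2.2 (39 of 83 stable, and by subtraction 10 progressive). Those patients had relapsed or refractory disease and different dosing, and the split would miss everyone who receives dexamethasone after a later progression. A range is safer.

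**The consequence is limited.** This is a descriptive secondary endpoint, and no test or stopping rule is tied to regimen. That caps the importance but does not supply the missing analysis.

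**Conclusion.** The point holds in this form: Section 12.2.3 specifies no adverse event summary by regimen at onset, so the tables as planned do not answer the safety part of objective 2 or give the combination profiles in endpoint 2. An event confined to one combination would appear at one-fifth to one-half of its rate there, assuming that 20-50% of treated patients receive that combination and that the event does not occur elsewhere. Some dilution occurs at any fraction below 100%. The primary endpoint is not affected. The sponsor should correct this before the final analysis. Accrual has closed, but the Amendment 6 rationale says a manuscript is still to come, so the change remains possible.

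**What to change.** In Section 12.2.3:

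1. Add adverse event incidence and worst grade by regimen at onset: lenalidomide alone, lenalidomide with prednisone, and lenalidomide with dexamethasone.
2. Count each subject once per event within each regimen. Use as denominator the patients exposed to that regimen, and give exact 95% confidence intervals.
3. Keep the pooled table as a co-equal summary of the whole strategy.
4. If rates per patient-cycle are added because exposure differs greatly between regimens, stop both events and exposure at April 2016 for non-serious events. Section 9.6.2 and footnote 12 of the assessment schedule say that only serious events are collected after that. Without the cutoff, later cycles would add exposure with no chance of a recorded non-serious event.

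The cost is a little more programming, with no new patients or procedures. Adverse events are already queried during treatment and when a steroid is added (Section 2), and reports carry administration dates. The small groups will give wide intervals, as the table above shows; that is the precision the trial has for each combination.

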# 12.2.4 Evaluation of the group difference between participants from Moffitt and South Korea

The study participants will be enrolled half from Moffitt and half from multiple sites in South Korea. The important demographic and clinical characters associated with the endpoints were addressed in the inclusion and exclusion criteria so these two groups should be comparable at baseline. Although there are currently no reports suggesting a difference tolerance or response in Korean patients to lenalidomide as compared to Version. 6 date 4/15/2016

Page 68 of 86 Confidential

European / North American patients, we will evaluate the ethnic effect for our study endpoints for conservative purpose. For survival endpoints (PFS and OS), the log-rank test will be applied to evaluate the ethnic effect. For response rate and adverse event proportion, the Fisher's exact test will be applied for testing the ethnic effect. If there are no significant differences between these two groups, we will provide the overall results using the combined data sources. If ethnic effects are observed for some endpoints, statistical models will be applied for adjusting the ethnic effect. Cox regression models and logistic models will be applied for adjusting the ethnic effect for the survival and binary endpoints, respectively.

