## **Prescribing Information**

Lenalidomide (Revlimid®) will be provided to research subjects for the duration of their participation in this trial at no charge to them or their insurance providers. Lenalidomide will be provided in accordance with the RevAssist® program of Celgene Corporation. Per standard RevAssist® requirements all physicians who prescribe lenalidomide for research subjects enrolled into this trial, and all research subjects enrolled into this trial, must be registered in and must comply with all requirements of the RevAssist® program. Prescriptions must be filled within 7 days. Only enough lenalidomide for one cycle of therapy will be supplied to the patient each cycle.

The planned dose of lenalidomide for investigation is 25 mg/day, orally on days 1 - 21 followed by 7 days rest (28 day cycle). Dosing will be based on CrCl:

Lenalidomide will be given at a dose of 25 mg once daily on days 1 to 21, every 28 days for those patients with a subjects with a creatinine clearance of  $\geq$  60 mL/min by Cockroft-Gault formula.

Subjects with a creatinine clearance of  $\geq$  30 mL/min but < 60 mL/min by Cockroft-Gault formula will begin lenalidomide at 10 mg once daily on days 1 to 21, every 28 days. The lenalidomide dose may be increased to dose 15 mg at the start of Cycle 3 if hematologic

toxicities have not occurred.

Page 34 of 86 Confidential

Dosing will be in the morning at approximately the same time each day. Lenalidomide capsules should be swallowed whole, and should not be broken, chewed or opened.

If a dose of lenalidomide is missed, it should be taken as soon as possible on the same day. If it is missed for the entire day, it should not be made up.

Patients who take more than the prescribed dose of lenalidomide should be instructed to seek emergency medical care if needed and contact study staff immediately.

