# Appendix VI: Cockcroft-Gault estimation of CrCl:

Cockcroft-Gault estimation of creatinine clearance (CrCl): (Cockcroft, 1976; Luke 1990)

CrCl (mL/min) = (140 - age) x (weight, kg) x 0.85 (Females) 72 x (serum creatinine, mg/dL) Page 85 of 86 Confidential

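### Section 12.2.4 presumes the Moffitt and Korean groups comparable from eligibility and reads an unadjusted difference as ethnic, although the clearance and starting-dose mix is left free to differ

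*Combined protocol and SAP*

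**What the plan says.** The synopsis plans about 30 patients at Moffitt and 30 in a parallel study of the same design at South Korean sites. Section 12.2.4 compares the two sets.

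- **Premise.** Because the relevant characteristics were covered by the entry criteria, the section concludes "so these two groups should be comparable at baseline".
- **Tests.** For PFS and OS, "the log-rank test will be applied to evaluate the ethnic effect". For response and adverse-event proportions, "the Fisher's exact test will be applied for testing the ethnic effect". No stratification or covariate is named.
- **Consequence.** If nothing is significant, combined results are given. If an effect is seen, "Cox regression models and logistic models will be applied for adjusting the ethnic effect for the survival and binary endpoints, respectively".

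The dosing rule lies elsewhere. Inclusion criterion 11 admits a calculated clearance of 30 mL/min or more. Under Prescribing Information, patients at 60 mL/min or above start at 25 mg, and those from 30 to below 60 "will begin lenalidomide at 10 mg once daily on days 1 to 21, every 28 days", with a possible rise to 15 mg at Cycle 3. Appendix VI gives the Cockcroft-Gault formula, which uses age, weight, sex and serum creatinine.

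**The concern.** Entry criteria set the edges of a population. They do not equalise what lies between them, and both starting-dose groups lie inside. If the studies enrolled patients of different weight, age, sex mix or renal function, their shares starting at 10 mg would differ. If outcome also differs between those starting-dose groups, a plain log-rank or Fisher comparison carries that difference under the label of ethnicity. In the opposite direction, the mix could mask a real group difference.

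The later Cox and logistic models do not help. They adjust the study result for group; they do not adjust the group contrast for clearance or dose. The contrast is also defined by study and site, so country and care setting travel with it.

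At stake are how any difference is described and whether results are presented as simply combined or as group-adjusted.

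**Working it through.** **1. The plan's own figure.** Section 12.1 expects 85% 12-month PFS in 60 patients, that is 0.85 × 60 = 51. The exact binomial interval for 51/60 is 73.4-92.9%, as stated. The plan gives no power for the Moffitt-Korea comparison, so there is no such figure to reproduce.

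**2. Can ordinary variation cross the dose cut?** Appendix VI: clearance = (140 − age) × weight × (0.85 if female) / (72 × creatinine). The patients below are illustrative, with creatinine 1.0 mg/dL.

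- Man, 75 years, 80 kg: 65 × 80 / 72 = 72.2 mL/min (25 mg start).
- Man, 75 years, 60 kg: 65 × 60 / 72 = 54.2 mL/min (10 mg start).
- Weight at the cut, age 75: 60 × 72 / 65 = 66.5 kg for a man; 66.5 / 0.85 = 78.2 kg for a woman.
- Age alone, man of 70 kg: 70 × 70 / 72 = 68.1 at age 70; 60 × 70 / 72 = 58.3 at age 80.

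So eligible patients fall on either side of 60 mL/min through weight, age or sex alone.

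**3. Size under stated assumptions.** Let q be the share starting at 10 mg. A group's response rate is (1 − q) × 60% + q × (rate at 10 mg), with no group effect within a starting-dose group. The spurious difference is (q₂ − q₁) × (gap between doses). Assumed: q₁ = 20%; q₂ = 40, 50 or 60%; gap 20 or 30 points. Fisher's test is taken as two-sided at 0.05 (the plan states no level), 30 per group, by full enumeration.

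| Gap | q₁ v q₂ | Response | Difference | Fisher rejects |
|---|---|---|---|---|
| 20 | 20 v 40% | 56 v 52% | 4 points | 3.4% |
| 20 | 20 v 50% | 56 v 50% | 6 points | 4.4% |
| 20 | 20 v 60% | 56 v 48% | 8 points | 5.8% |
| 30 | 20 v 40% | 54 v 48% | 6 points | 4.4% |
| 30 | 20 v 50% | 54 v 45% | 9 points | 6.7% |
| 30 | 20 v 60% | 54 v 42% | 12 points | 10.1% |

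With equal shares the rate is 2.7%, because Fisher's test is conservative at this size. With a gap of only 10 points it is 2.8-3.4%. A wider assumed range (shares from 30 v 50% to 20 v 70%; gaps of 20 to 40 points, for response or for 12-month PFS treated as a proportion) gives differences of 4-20 points and rejection of 3-31%.

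**4. Does stratifying remove it?** Simulation, 20,000 runs per case, Mantel-Haenszel test, no group effect within dose:

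| Rate at 25 / 10 mg | Shares at 10 mg | Unstratified | Stratified |
|---|---|---|---|
| 60 / 30% | 30 v 50% | 7.9% | 5.0% |
| 60 / 20% | 25 v 60% | 19.6% | 4.9% |
| 90 / 70% | 25 v 60% | 10.3% | 4.9% |

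**5. A non-significant result.** At 30 per group, Fisher's test detects 85% v 60% only 49% of the time. Non-significance therefore does not show that the groups are alike.

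No log-rank calculation was made; the size for PFS and OS as times to event is not quantified.

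**The case against.** The strongest reply is that this is a secondary check, made out of caution before combining two studies of the same design. Ethnicity is not among the study's objectives or endpoints. For pooling the strategy as delivered, clearance-based dosing included, the unadjusted difference is the relevant quantity, and stratifying could remove heterogeneity that matters. That stands, and it is why the unadjusted comparison should stay.

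It is also fair that the inputs are assumed. A reader might infer that one group was lighter and mostly started at 10 mg; the documents give no weight, clearance or dose mix by group. A reader might infer that a 10 mg start means a worse outcome; no outcome by dose is given. The protocol reports that about two-thirds of the drug leaves unchanged in urine, so 10 mg at low clearance is not simply lower exposure. The possible rise at Cycle 3 and the added steroids could dilute a starting-dose effect further.

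Some cover exists already. The section heading speaks of a group difference, and section 12 summarises baseline characteristics. Section 12.2.2 allows covariate models for response and OS, but they are optional, name no covariate and are not tied to this contrast. Its text breaks off where PFS under single-agent lenalidomide is taken up, so nothing firm can be said about PFS covariates there.

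Finally, one two-level stratum cannot isolate ethnicity. That is correct, and it argues against the ethnic label with or without adjustment.

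**Conclusion.** The point holds in a limited form. Comparability does not follow from the entry criteria, and an unadjusted study contrast cannot be read as an ethnic effect when clearance and starting dose are free to differ. The protocol's own cut and formula show how such a difference could arise.

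The size rests on assumed dose shares and an assumed outcome gap. In the main range the spurious response difference is 4-12 points and Fisher's rejection rate 3.4-10.1%. Three of the six scenarios stay below 5%, and the highest needs both extremes together.

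Two stronger readings are not supported. A reader might infer that a false ethnic finding is likely; neither the existence nor the direction of an imbalance is shown. A reader might infer that the primary 12-month PFS estimate is invalid; section 12.2.1 defines it over all treated patients, and this point concerns only how the two groups are compared and described. Nothing here bears on whether the dosing rule is right. This is a cheap improvement worth making.

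**What to change.** In section 12.2.4:

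1. Delete the statement that eligibility makes the groups comparable.
2. Call the contrast a Moffitt-Korea study/site difference and do not attribute it to ethnicity.
3. Tabulate weight, clearance and starting-dose group by study.
4. Keep the unadjusted comparison to describe the pooling. Beside it, report a comparison stratified by baseline clearance/starting-dose group (30 to below 60 v 60 mL/min or more): stratified log-rank for PFS and OS, and an exact stratified Cochran-Mantel-Haenszel test with common odds ratio for response and adverse events. Use the baseline group, not later dose.
5. State that other site differences remain confounded with group.

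The cost is revised wording, one extra set of results and some loss of precision from two strata (expected to be slight; not calculated). The stratum is already needed for eligibility and dosing; that the Korean study recorded it is assumed from its identical design. Accrual at Moffitt is closed, so if the comparison has already been run, the stratified result should be labelled as added afterwards.

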- CBC with diff. is required on Day 1Cycle 1 (unless baseline done within 7 days of Day 1), then every 2 weeks for the first 4 weeks of therapy. After the first 4 weeks of therapy, if the patient required a dose reduction of lenalidomide (Revlimid®) or the addition of cytokine support due to neutropenia encountered during the previous cycle, CBC with diff. is required at least every 2 weeks during the next cycle, otherwise CBC with diff. is required at least every 4 weeks. More frequent CBCs may be obtained at the investigator's discretion. After 4/2016, laboratory testing is at the discretion of the treating physician and in accordance with lenalidomide package insert. CBC will not be collected for the purpose of the trial but could be ordered per standard practise
-  Lenalidomide must be prescribed through and in compliance with Celgene's RevAssist® Program. Prescriptions must be filled within 7 days. Drug returned from the previous cycle will be counted, recorded in the patient's CRF. Patients must be instructed to return all bottles (whether empty, partial or full) at each visit. Unused lenalidomide should be returned to the patient for disposition in accordance with the RevAssist® program. After April 2016, diaries and pill counts will not be performed.
- 11. During maintenance, patients will have laboratory testing per institutional standard of care approximately every 3 months.
- 12 After April 2016, only serious adverse events SAE will be collected.
- 13 At the initiation of study and yearly thereafter.
- 14 Ancillary bone marrow aspiration will be obtained at baseline and after 2 months of lenalidomide monotherapy. Ancillary peripheral blood samples will be obtained at baseline, after 2 months of lenalidomide monotherapy and after 2 month of addition of dexamethasone .see section 9.7.4 for details regarding ancillary studies.
- 15. Patients who complete the first 6 cycles of therapy, are on a stable dose of lenalidomide for more than 2 cycles and are responding to therapy are eligible for entering a maintenance schedule of visits where office visits will be every 3 months and monitoring will be pre institutional standard of care Patient will continue to be followed for disease progression per standard clinical practice.

Page 11 of 86 Confidential

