## 9.6.2. Adverse Event Reporting

Lenalidomide was approved by the FDA for newly diagnosed multiple myeloma patients in 2/2015. MCC16018 involves lenalidomide based therapy for newly diagnosed multiple myeloma and is thus currently considered standard of care (although that use was considered investigational Version. 5.1 date 6/25/2014

Page 55 of 86 Confidential

at the time of initiation and completion of accrual of the study). Moreover, the adverse event profile of lenalidomide is now well established. Finally, as of April 2016, all the current study patients have been on present therapy for a minimum of 2 years and a continued collection of all adverse events will not leads to a meaningful change in the adverse event profile of lenalidomide. Accordingly, as of April 2016, we will only collect serious adverse events (SAE) and will no longer collect other adverse events encountered after that time.

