## 12.1. Sample size:

The primary endpoint is 12-month PFS for the overall response adaptive approach. Based on the E4A03 and SWOG 2032 studies, the 12-month PFS is approximately 70% for patients treated with lenalidomide low dose dexamethasone. The sample size determination is primarily based on the consideration of providing an estimate of the 12-month PFS with reasonable precision. We estimate the 12-month PFS in the response adapted approach is 85%. With a sample size of 60 evaluable patients (30 from Moffitt and 30 from sites in South Korea), its 95% confidence interval is 73.4-92.9%.

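### The Moffitt–Korea adverse event comparison in section 12.2.4 has no common time window or exposure adjustment, so unequal time on drug or local monitoring can be read as an ethnic difference in tolerance, or can hide one

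*Combined protocol and SAP*

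**What the plan says.** Section 12.2.4 sets out the only between-group comparison of harms in the plan: "For response rate and adverse event proportion, the Fisher's exact test will be applied for testing the ethnic effect". What follows depends on the result: "If there are no significant differences between these two groups, we will provide the overall results using the combined data sources"; otherwise a logistic model adjusts binary endpoints for the ethnic effect. Neither time on drug nor monitoring is named as a covariate. For PFS and OS the same section uses the log-rank test.

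The adverse event proportion comes from section 12.2.3, which covers everyone who takes any study drug and in which "a subject having the same event more than once will be counted only once". No time limit is given. The synopsis lets treatment run until progression on lenalidomide plus low dose dexamethasone, unacceptable toxicity or withdrawal of consent.

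The schedule in section 2 has a 4-weekly column for the first 6 cycles. Responders on a stable dose may then move to 3-monthly visits, and footnote 11 says: "During maintenance, patients will have laboratory testing per institutional standard of care approximately every 3 months". Section 9.6.2 adds that "as of April 2016, we will only collect serious adverse events (SAE) and will no longer collect other adverse events encountered after that time". The synopsis describes the Korean patients as a parallel study of identical design; it gives no accrual dates, follow-up or local monitoring practice for them.

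**The concern.** A crude proportion of patients who ever had an event depends on how long each patient was observed and how often anyone looked. If one cohort stays on drug longer or is tested more often after cycle 6, it will show more events even when tolerance is the same. The plan would label that an ethnic effect.

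The design supplies a route for this. Entry to maintenance requires response, and time on drug ends at progression or toxicity. If efficacy differs between cohorts, which section 12.2.4 considers worth testing, time at risk and monitoring intensity would be expected to differ too. The log-rank test allows for unequal follow-up in the survival endpoints; the adverse event test has no counterpart.

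At stake are whether adverse event data are pooled or adjusted, and any published statement about how Korean patients tolerate lenalidomide.

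**Working it through.** **The plan's own figure.** Section 12.1 gives no calculation for the between-cohort test. Its one precision statement reproduces: 85% of 60 is 51, and the exact binomial interval for 51/60 is 73.43% to 92.90%, against the stated 73.4–92.9%.

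**Inputs from the documents.** 30 patients per cohort (section 12.1); Fisher's exact test (12.2.4); ever/never counting (12.2.3); six 28-day cycles on the 4-weekly schedule, so 168 days, or 168/30.44 = 5.52 months.

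**Assumptions.** Two-sided 0.05, since no level is stated. First-event hazard h of 2–10% per month, in 1-point steps, identical in both cohorts. After cycle 6 it is multiplied by f = 1, 1/3 or 1/5. Everyone in a cohort has the same time on drug. The documents give none of these values.

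**Formula.** Probability of an event by month t: F(t) = 1 − exp(−[h × min(t, 5.52) + f × h × max(t − 5.52, 0)]). The rejection probability sums the binomial probabilities of all 2×2 tables with Fisher p < 0.05.

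**Worked cases, 12 versus 24 months, no true difference.**
- h = 3%, constant: 1 − exp(−0.36) = 30.2% against 1 − exp(−0.72) = 51.3%; rejection 28.8%.
- h = 8%, constant: 61.7% against 85.3%; rejection 44.8%, the highest in the grid (44.1% at h = 7%).
- h = 2%, falling to one fifth: exponents 0.136 and 0.184, so 12.7% against 16.8%; rejection 2.8%, the lowest.

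**Whole grid.**

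| Hazard after cycle 6 | Spurious difference, 12 v 24 months | Fisher rejects, 12 v 24 | Fisher rejects, 12 v 18 | Fisher rejects, 12 v 12 |
|---|---|---|---|---|
| unchanged | 17–25 points | 21–45% | 7–16% | 2.3–2.7% |
| one third | 7–15 points | 5–15% | 3–6% | 1.6–2.7% |
| one fifth | 4–11 points | 3–9% | 2–4% | 1.4–2.7% |

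**Unequal monitoring instead of unequal time.** Both cohorts have 24 months on drug and a constant hazard, set so that 10%, 20% or 30% have the event within 6 cycles. If one cohort detects only 75% of events after cycle 6, rejection is 4–6%; at 50% it is 11–22%; at 25% it is 29–61%.

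**Masking.** A cohort with twice the hazard but half the time on drug shows no difference: 3% per month for 24 months and 6% per month for 12 months both give 1 − exp(−0.72) = 51.3%. Within 6 cycles the same hazards give 15.3% and 28.2%. Even with equal follow-up the test is weak: 80% power at 30 per group needs about 20% against 58%.

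**April 2016 change.** Six of the 30 Moffitt patients were still on treatment. With 30–70% already affected, and a 10–50% chance of a later uncollected first event in those of the six not yet affected, rejection is 2.6–5.1%, against 2.6–2.7% under the null.

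**Restricting to cycles 1–6.** With equal hazards and everyone observed for six cycles, rejection is 1.0–2.6% whatever happens later. The price is the share of first events beyond cycle 6, [F(T) − F(5.52)]/F(T): 14–51% over T = 12 months, 30–73% over 24 and 38–80% over 36.

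**The case against.** Nothing in the documents shows that the cohorts differed. They nominally share one design and one 3-monthly maintenance schedule, and section 8.1.5 asks for adverse events at every visit. Crude incidence with Fisher's test is conventional in a 60-patient phase 2 study, the comparison is a cautionary side check, and because pooling is decided endpoint by endpoint, an adverse event result does not touch the primary PFS estimate. A twofold gap in time on drug is an assumption; at 12 versus 18 months with a falling hazard, rejection is only 2–6%.

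Most of this stands, and it limits the size of the point. It does not remove it: the plan neither secures equal time and monitoring nor corrects for their absence, yet names the result ethnic.

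Two stronger readings are tempting and are not supported.
- A reader might infer that harms are ascertained identically in cycles 1–6 and only there. Footnote 9 of the schedule allows extra blood counts at the investigator's discretion and more frequent ones after a dose reduction or cytokine support. What the cohorts share in that period is a mandated minimum. After cycle 6, like ascertainment is not assured; the documents do not show that it was unlike.
- A reader might see the April 2016 change as a main source of bias. It affects six Moffitt patients already 2–4 years on drug and adds little in the calculation above.

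**Conclusion.** The point holds as a weakness in a secondary comparison. As written, the test cannot separate tolerance from time on drug or local monitoring. With identical hazards it rejects in about 3–45% of trials at 12 versus 24 months and 2–16% at 12 versus 18, against about 1–3% with equal time. The upper ends need a hazard that stays constant after cycle 6; where it falls to one fifth, even a twofold gap gives no more than about 9%. For monitoring alone, roughly half of the later events would have to be missed in one cohort before rejection reaches 11–22%.

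All of this rests on assumed hazards, durations and detection fractions and on an assumed two-sided 0.05. It would be wrong to conclude that a false ethnic effect is likely, or that the Korean data were followed differently: the documents contain no Korean follow-up. The change is worth making because it is cheap and the planned label claims more than the comparison can show.

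**What to change.** In section 12.2.4:
- Base the between-cohort adverse event comparison on events with onset in cycles 1–6, counted from the first lenalidomide dose, the period with the same protocol-mandated minimum schedule.
- Analyse it by time to first event or by person-time, so that patients who stop before the end of cycle 6 are handled.
- For the whole treatment period, report time on drug and exposure-adjusted event rates by cohort, so that late events stay visible.
- Leave the whole-study tables of section 12.2.3 descriptive, with no test between cohorts.
- Describe any difference as between-cohort, not ethnic.

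The April 2016 change should not affect the Moffitt window: the last enrolment, in 6/2013, was about 34 months earlier, and six cycles take about 5.5 months unless delays are very long.

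The cost is SAP wording, with no new visits or patients. It needs event onset and dosing dates from both cohorts; the documents do not confirm these for the Korean data, so check that first. The real downside is that late first events, 30–73% of first events over 24 months under the assumptions above, would be described but not formally tested between cohorts.
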